Appendix M – Neurocognitive Battery Record

Study Number: _____

PID: _____

Investigator: [name].

Date: ____ / ____ / ____

Instructions: Complete the table below to track date of neurocognitive testing and assessments performed.

V1 Test Date: ____ / ____ / ____	Test Name:	Completed:	If not completed, state reason
	Digit Span (DS)	Yes  No 	
	Letter Number Sequencing (LNS)	Yes  No 	
	Matrix Reasoning (MR)	Yes  No 	
	Symbol Search (SS)	Yes  No 	
	Coding (CD)	Yes  No 	
	Controlled Oral Word Association Test (COWAT)	Yes  No 	
	Trail Making Test Parts A and B (TMT A & B)	Yes  No 	
	Montreal Cognitive Assessment (MoCA)	Yes  No 	
	Total Score		

V3 Test Date: ____ / ____ / ____	Test Name:	Completed:	If not completed, state reason
	Digit Span (DS)	Yes  No 	
	Letter Number Sequencing (LNS)	Yes  No 	
	Matrix Reasoning (MR)	Yes  No 	
	Symbol Search (SS)	Yes  No 	
	Coding (CD)	Yes  No 	
	Controlled Oral Word Association Test (COWAT)	Yes  No 	
	Trail Making Test Parts A and B (TMT A & B)	Yes  No 	
	Montreal Cognitive Assessment (MoCA)	Yes  No 	
	Total Score		

Appendix N – FACT Br (Version 4)

Study Number: _____ PID: _____
Investigator: [name]. Date: ____ / ____ / ____

Below is a list of statements that other people with your illness have said are important. **Please circle or mark one number per line to indicate your response as it applies to the past 7 days.**

PHYSICAL WELL-BEING		Not at all	A little bit	Some- what	Quite a bit	Very much
GP1	I have a lack of energy.....	0	1	2	3	4
GP2	I have nausea.....	0	1	2	3	4
GP3	Because of my physical condition, I have trouble meeting the needs of my family.....	0	1	2	3	4
GP4	I have pain.....	0	1	2	3	4
GP5	I am bothered by side effects of treatment.....	0	1	2	3	4
GP6	I feel ill.....	0	1	2	3	4
GP7	I am forced to spend time in bed	0	1	2	3	4

SOCIAL/FAMILY WELL-BEING		Not at all	A little bit	Some- what	Quite a bit	Very much
GS1	I feel close to my friends	0	1	2	3	4
GS2	I get emotional support from my family.....	0	1	2	3	4
GS3	I get support from my friends	0	1	2	3	4
GS4	My family has accepted my illness.....	0	1	2	3	4
GS5	I am satisfied with family communication about my illness	0	1	2	3	4
GS6	I feel close to my partner (or the person who is my main support)	0	1	2	3	4
Q1	Regardless of your current level of sexual activity, please answer the following question. If you prefer not to answer it, please check this box and go to the next section.					
GS7	I am satisfied with my sex life.....	0	1	2	3	4

By circling one (1) number per line, please indicate how true each statement has been for you during the past 7 days

EMOTIONAL WELL-BEING		Not at all	A little bit	Some- what	Quite a bit	Very much
GE1	I feel sad.....	0	1	2	3	4
GE2	I am satisfied with how I am coping with my illness	0	1	2	3	4
GE3	I am losing hope in the fight against my illness	0	1	2	3	4
GE4	I feel nervous	0	1	2	3	4
GE5	I worry about dying	0	1	2	3	4
GE6	I worry that my condition will get worse.....	0	1	2	3	4

FUNCTIONAL WELL-BEING		Not at all	A little bit	Some- what	Quite a bit	Very much
GF1	I am able to work (include work at home).....	0	1	2	3	4
GF2	My work (include work at home) is fulfilling	0	1	2	3	4
GF3	I am able to enjoy life	0	1	2	3	4
GF4	I have accepted my illness	0	1	2	3	4
GF5	I am sleeping well.....	0	1	2	3	4
GF6	I am enjoying the things I usually do for fun.....	0	1	2	3	4
GF7	I am content with the quality of my life right now.....	0	1	2	3	4

By circling one (1) number per line, please indicate how true each statement has been for you during the past 7 days.

	ADDITIONAL CONCERNS	Not at all	A little bit	Some-what	Quite a bit	Very much
Br1	I am able to concentrate.....	0	1	2	3	4
Br2	I have had seizures (convulsions)	0	1	2	3	4
Br3	I can remember new things.....	0	1	2	3	4
Br4	I get frustrated that I cannot do things I used to	0	1	2	3	4
Br5	I am afraid of having a seizure (convulsion)	0	1	2	3	4
Br6	I have trouble with my eyesight.....	0	1	2	3	4
Br7	I feel independent	0	1	2	3	4
NTX 6	I have trouble hearing	0	1	2	3	4
Br8	I am able to find the right word(s) to say what I mean.....	0	1	2	3	4
Br9	I have difficulty expressing my thoughts.....	0	1	2	3	4
Br10	I am bothered by the change in my personality.....	0	1	2	3	4
Br11	I am able to make decisions and take responsibility.....	0	1	2	3	4
Br12	I am bothered by the drop in my contribution to the family	0	1	2	3	4
Br13	I am able to put my thoughts together	0	1	2	3	4
Br14	I need help in caring for myself (bathing, dressing, eating, etc.).....	0	1	2	3	4
Br15	I am able to put my thoughts into action	0	1	2	3	4
Br16	I am able to read like I used to.....	0	1	2	3	4
Br17	I am able to write like I used to	0	1	2	3	4
Br18	I am able to drive a vehicle (my car, truck, etc.)	0	1	2	3	4
Br19	I have trouble feeling sensations in my arms, hands, or legs.....	0	1	2	3	4
Br20	I have weakness in my arms or legs	0	1	2	3	4
Br21	I have trouble with coordination.....	0	1	2	3	4

Open Label Safety Study of Solriamfetol to Promote Wakefulness and Improve Cognition and Quality of Life in Patients with Primary

Gliomas

Wake Forest Baptist Comprehensive Cancer Center

WFBCCC 98418

I get headaches..... 0 1 2 3 4

Appendix O – Concurrent Medications Form

Study Number: _____ PID: _____
PI: [name]. _____ Date (mm/dd/yyyy): _____/_____/_____

Instructions: Fill this form out at the baseline/pre-study visit and/or additional visits per protocol.

Study Visit (if needed per protocol):

- Baseline
- Visit 1
- Visit 2
- Visit 3
- Other visit: (please specify) _____

Current Medications List

Prescription Medications:

Appendix P – Off-Study Form

Study Number: _____ PID: _____

Investigator: [name]. Date: ____ / ____ / ____

Instructions: Complete this form if the patient either withdraws consent or is removed from the study.

Name of Person Completing form _____

Did the subject meet eligibility criteria for study enrollment? Yes No

Was the subject removed from the study per physician decision? Yes No
(if yes, move to #5)

Did the patient withdraw consent to participate in the study? Yes No
(if yes move to #1)

Reason for patient withdrawal:

1. Unacceptable toxicity from solriamfetol
2. Did not want to participate anymore. Reason:

3. Other: _____

4. Please specify what portion of the study the subject wishes to withdraw from:

For just the solriamfetol administration only
 For all components of the research study (including follow up in the medical record)

Reason(s) for Removal:

5. Patient exhibited progression of disease
6. Unacceptable toxicity from solriamfetol
7. Investigator's discretion to withdraw patient from the study because continued participation in the study is not in the patient's best interest (*Describe below)
8. Undercurrent illness: a condition, injury, or disease unrelated to the intended disease for which the study is investigating, that renders continuing the treatment unsafe or regular follow-up impossible (*Describe below)
9. General or specific changes in the patient's condition that renders the patient ineligible for further investigational treatment (*Describe below)
10. Non-compliance with investigational treatment, protocol-required evaluations or follow-up visits (*Describe below)

Open Label Safety Study of Solriamfetol to Promote Wakefulness and Improve Cognition and Quality of Life in Patients with Primary Gliomas
Wake Forest Baptist Comprehensive Cancer Center
WFBCCC 98418

11. Termination of the clinical trial by the clinical sponsor

Comment:

If reason for withdrawal includes #7, 8, 9, or 10 then please add comments clarifying this information) _____

Appendix Q – MR Imaging Record

Study Number: _____ PID: _____

Investigator: [name]. Date: ____ / ____ / ____

Instructions: Complete the table below to track date of MRI Brain throughout the study.

Date of Enrollment: ____ / ____ / ____

Off Study Date: ____ / ____ / ____

Please record the date of any MR imaging between the date of enrollment and off study dates. If there is no imaging in between these times, please record the date of the next MR imaging after the off study date. If there is no imaging available, please list the reason.

Date of neuroimaging	Completed:	If not completed, state reason
____ / ____ / ____	Yes  No 	
____ / ____ / ____	Yes  No 	
____ / ____ / ____	Yes  No 	
____ / ____ / ____	Yes  No 	
____ / ____ / ____	Yes  No 	
____ / ____ / ____	Yes  No 	

Appendix R – Sleep Diary and Actigraphy Record

Week of _____	Day 1	Day 2	Day 3	Day 4	Day 5	Day 6	Day 7
Actigraph worn?	 Yes  No						
Did you take a nap?	 Yes  No						
How long did you nap?							
Time you fell asleep:	AM/PM						
Time you woke up:	AM/PM						
Did you take anything to help you sleep at night?	 Yes  No						
If so, indicate amount:							
Prescribed medicine							
Over-the-counter							
Alcohol							
Time you entered bed?	AM/PM						
Minutes/hours it took you to fall asleep?							
Number of times you awoke during the night?							
Time it took you to fall back asleep:							
First awakening	HR MIN						
Second awakening	HR MIN						
Third awakening	HR MIN						
Fourth awakening	HR MIN						
Fifth awakening	HR MIN						
Sixth awakening	HR MIN						
Indicate time you woke up:	AM/PM						
Indicate time you got out of bed:	AM/PM						
Falling asleep last night was:	 Extremely difficult  Difficult  Fair  Easy  Very Easy	 Extremely difficult  Difficult  Fair  Easy  Very Easy	 Extremely difficult  Difficult  Fair  Easy  Very Easy	 Extremely difficult  Difficult  Fair  Easy  Very Easy	 Extremely difficult  Difficult  Fair  Easy  Very Easy	 Extremely difficult  Difficult  Fair  Easy  Very Easy	 Extremely difficult  Difficult  Fair  Easy  Very Easy
Staying asleep last night was:	 Extremely difficult  Difficult  Fair  Easy  Very Easy	 Extremely difficult  Difficult  Fair  Easy  Very Easy	 Extremely difficult  Difficult  Fair  Easy  Very Easy	 Extremely difficult  Difficult  Fair  Easy  Very Easy	 Extremely difficult  Difficult  Fair  Easy  Very Easy	 Extremely difficult  Difficult  Fair  Easy  Very Easy	 Extremely difficult  Difficult  Fair  Easy  Very Easy
Rate the quality of sleep for this night:	 Extremely difficult  Difficult  Fair  Easy  Very Easy	 Extremely difficult  Difficult  Fair  Easy  Very Easy	 Extremely difficult  Difficult  Fair  Easy  Very Easy	 Extremely difficult  Difficult  Fair  Easy  Very Easy	 Extremely difficult  Difficult  Fair  Easy  Very Easy	 Extremely difficult  Difficult  Fair  Easy  Very Easy	 Extremely difficult  Difficult  Fair  Easy  Very Easy
Rate your sleep this night compared to other nights:	 Extremely difficult  Difficult  Fair	 Extremely difficult  Difficult  Fair	 Extremely difficult  Difficult  Fair	 Extremely difficult  Difficult  Fair	 Extremely difficult  Difficult  Fair	 Extremely difficult  Difficult  Fair	 Extremely difficult  Difficult  Fair

 Easy						
 Very Easy						

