4. Preliminary Data on Sleep-Wake Disturbance in Gliomas and Rationale for Solriamfetol

At the American Academy of Neurology Annual Meeting, we recently presented the results of a pilot cross-sectional study evaluating the prevalence, risk factors, associated symptoms, and quality of life impact of self-reported sleep-wake disturbances in a cohort of patients with primary gliomas (Figure 2).

Figure 2: Study design from the prior cross-sectional study of sleep disorders in brain tumors patients

[figure not shown]

Figure 3: Prevalence of patient-reported excessive daytime sleepiness by Epworth Sleepiness Scale (ESS) scores

A prospective cohort of 50 brain tumor patients was recruited to complete a one-time survey-based assessment of self-reported sleep disturbance using the Epworth Sleepiness Scale (ESS), Pittsburgh Sleep Quality Index (PSQI), a previously validated sleep hygiene and sleep habits questionnaire, as well as clinical and treatment

[figure not shown]
characteristics, and quality of life (e.g. EQ-5D). In this study, excessive daytime sleepiness (EDS, ESS \geq 10) was reported in 46% of brain tumor patients (Figure 3). Patient-reported ESS was generally correlated with caregiver observed ESS for the patient ($r=0.56$, $p=0.005$), though important differences were present at the extremes of patient ESS. Abnormally low ESS (ESS<5) was observed in 16% of patients, meaning that a normal ESS score was only observed in 36% of the cohort. Self-reported excessive daytime sleepiness (ESS \geq 10) was significantly more common in patients who had ever undergone chemotherapy (42% vs 22%, $p<0.008$) but not radiation therapy ($p=0.30$) or by tumor grade ($p=0.25$). Fifty-two percent of patients on active corticosteroids had ESS \geq 10 compared to only 28% of those not taking corticosteroids ($p=0.17$). Chemotherapy treatment was associated with nighttime awakenings ($p=0.04$) while corticosteroid use was associated with lower daytime energy ($p=0.04$). EDS was also associated with poorer health-related QOL including reduced mobility ($p<0.03$) and impaired daily activities ($p<0.02$). These preliminary data support that:

1. Sleep-wake disturbances in the form of patient-reported excessive daytime sleepiness are common in brain tumor patients
2. That patient ESS can be used to evaluate self-reported sleep dysfunction given the correlation with caregiver observation, and

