The main study assessments will be performed at baseline prior to flexible dose titration and then at the end of the fixed dose drug continuation phase. This will include: (1) patient reported measures, (2) objective measures of sleep activity, (3) neurocognitive functioning (4) assessment of associated symptoms such as fatigue, mood, and (5) quality of life. Additional assessment of patient-reported measures will be performed after dose escalation and prior to the fixed dose drug continuation. Due to practice effects and other issues related to repeated measurement, neurocognitive data will only be collected pre- and post-treatment.

Sleep diaries will be completed continuously throughout the ~10 week study. Seven-day actigraphy will be completed at each dose escalation and during the first and last weeks of fixed dose drug continuation.

Additional assessments will be performed as per the standard of care. In this population, it is standard of care for MR Brain to be performed roughly every 8-16 weeks. Data on tumor status by imaging (e.g. stable disease, imaging progression, etc) will be recorded prior to study treatment and following study treatment to assess for tumor progression as a factor contributing to changes in patient-reported and clinician assessed outcome measures.

Adverse events will be assessed every 7 days during flexible dose titration (via telephone) and at the end of the fixed dose treatment. Adverse event data will be compared to that reported in patients with narcolepsy.⁵⁰

Open Label Safety Study of Solriamfetol to Promote Wakefulness and Improve Cognition and Quality of Life in
 Patients with Primary Gliomas
 Wake Forest Baptist Comprehensive Cancer Center
 WFBCCC 98418

2. Study-Related Activities

	Pre-Study ^a ^k	Baseline Visit V1 (D1)	Begin Flexible Dose Titration (D8+1 dy)	Flexible Dose D7 (D15+1 dy)	Flexible Dose D14 (D22+1 dy)	Fixed Dose Initiation Visit V2 ^k (D29+7 dys)	End of Treatment Visit V3 (D70+7 dys)	30 day Follow Up Visit V4 ^k
Informed consent	X							
Demographics	X							
Medical history	X							
Concurrent meds	X					X	X	
Physical exam ¹		X				X	X	X
Vital signs ^b	X ^c	X				X	X	X
CBC w/diff, platelets	X					X	X	X
Serum chemistry ^d	X					X	X	X
B-HCG ^e	X							
Electrocardiogram (EKG)		X				X		
Adverse event evaluation		X	X ^f	X ^f	X ^f	X	X	X
Epworth Sleepiness Scale (ESS)	X	X ^g	X ^g	X ^g	X ^g	X ^g	X ^g	
Sleep Measures: Sleep diary, Actigraphy ^h		X ⁱ	X	X	X	X	X	

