Adverse events will be assessed by telephone call completed on D8+1 day, D15+1 day, and D22+1 day. Patients will be assessed in clinic at D29+7 days. Patients who report a symptomatic dose-limiting toxicity will de-escalate treatment back to the highest previously tolerated dose and will be seen for V2.

6. Fixed Dose Drug Continuation

At the completion of the flexible dose titration, patients will be seen for a routine study visit (V2) or via telehealth visit to document adverse events at the completion of flexible dosing, review sleep diary and actigraphy, and complete V2 assessments. Data from this interim time point may be used to clarify the trajectory of improvement, decline, and no change in study assessments. Patients will then proceed with fixed dose treatment at 300 mg p.o. once daily or the maximum tolerated dose for that patient.

Fixed dose drug continuation will be continued for 6 weeks. Patients will complete a sleep diary for the first 7 and last 7 days of fixed dose treatment; actigraphy will be collected continuously. At the completion of fixed dose treatment, patients will be seen for V3 study assessments (Section 6.7).

7. 30 Day Follow Up

All patients will be followed for 30 days following the completion of treatment to assess for delayed toxicity. Adverse events will be recorded at this 30 day follow up visit. If the patient is unable to return for this visit, adverse events will be recorded by telephone or telehealth visit.

8. Study Assessments

Assessment of sleep, neuro-cognitive function, fatigue, mood and quality of life will be assessed at baseline (V1) and at the end of the fixed-dose drug continuation phase of the study (V3). Given that patient drop out could occur during the course of the study treatment, study assessments that are not subject to significant practice and/or repeated measure effects will also be assessed after the flexible dose titration period (V2).

The following assessments will be performed:

1. Patient-reported outcome measures (PROMs) for sleep:

Changes in patient-reported outcomes measures (PROMs) are pivotal to cancer control drug approval.

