The ESS is an 8-item validated instrument (min score 0 – max score 24, Appendix H) that is easy to implement and an accepted screening tool for symptoms of excessive daytime sleepiness. It has been well studied in patients with EDS and brain tumors.^{7,13,45-47,51,52} An accepted cutoff of ESS^{>10} has been used to indicate EDS for enrollment into studies evaluating therapeutic interventions.⁵⁰ Prior studies have indicated that a 25% reduction in ESS may be useful as a threshold to identify patients who respond to solriamfetol treatment.⁵³

The PSQI is a 19-item validated self-report questionnaire (Appendix I) assessing sleep quality including subjective sleep quality, sleep latency, sleep duration, sleep efficiency,

and daytime dysfunction. Prior studies demonstrate impaired sleep quality in patients with cancer⁴⁰ and brain tumors.⁵²

The ESS and PSQI measure non-overlapping orthogonal dimensions of self-reported sleep-wake symptoms.⁵²

These measures will be completed prior to flexible dose titration, at the interim time point after flexible dose titration and before fixed dose continuation, and at end of treatment (see 7.2 Study-Related Activities).

2. Objective measures of sleep activity:

Actigraphy and sleep diaries are widely used, efficient, and affordable methods for measuring sleep-wake time.

Actigraphy has been shown to provide accurate data that is comparable to polysomnography⁵² and is increasingly used to provide an objective measure of sleep in clinical trials.⁵² Actigraph devices are worn on the wrist and record movements that can be used to estimate sleep patterns using specialized computer software programs. Completion of actigraphy will be recorded (Appendix R).

A 7-day sleep diary (Appendix R) will be provided to all patients at the time of consent and/or study enrollment. All sleep diaries will be collected over 7-days (i.e. 7-day sleep diary and 7-day actigraphy) including at pre-study baseline, throughout each dose of the dose escalation phase, and during the first 7-days and last 7-days of the fixed dose drug continuation phase of the study. Caregivers may complete sleep diaries for patients. Actigraphy will be collected continuously from baseline to end of treatment (see 7.2 Study-Related Activities).

3. Neurocognitive Battery:

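### Three sleep diary defects need correcting, though they do not void its pre-post analysis: two items have mismatched answer options, the reporter is not recorded, and the diary and actigraphy schedules are reversed between sections

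*Combined protocol and SAP*

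**What the plan says.** **Purpose.** Secondary objective 6 (Section 3.2) is the pre- versus post-treatment effect on sleep-wake times, measured by actigraphy and sleep diary. Section 6.2, outcome 6, describes the diary as patient-reported. Section 13.2 plans paired t or Wilcoxon signed rank tests for pre-post changes. Section 13.3.1 regresses actigraphy on dose.

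**Form.** Appendix R has four five-option rating items. The one that begins "Falling asleep last night was" and its staying-asleep companion run from extremely difficult to very easy. So do "Rate the quality of sleep for this night" and "Rate your sleep this night compared to other nights".

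**Reporter.** Section 7.8, item 2, states: "Caregivers may complete sleep diaries for patients". Appendix R as shown has no field for who filled it in.

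**Schedule.** Section 7.1 says "Sleep diaries will be completed continuously throughout the ~10 week study" and "Seven-day actigraphy will be completed at each dose escalation and during the first and last weeks of fixed dose drug continuation". Section 7.6 says "Patients will complete a sleep diary for the first 7 and last 7 days of fixed dose treatment; actigraphy will be collected continuously". Section 7.2 footnote h and the last sentences of Section 7.8, item 2, agree with Section 7.6. Earlier in the same paragraph of Section 7.8, however, actigraphy is described as a 7-day record.

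**The concern.** The diary is one of two instruments for a named secondary objective, and two of the defects cannot be repaired once data are collected.

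- An ease-or-difficulty answer does not say whether sleep was good or bad. The comparison item has no better, same or worse option. These are the diary's only overall quality and comparison ratings.
- The planned analysis is paired within patient. If the patient reports at baseline and a caregiver in the last week, the difference between reporters is mixed with the treatment change. The exposed fields are those a bystander often cannot observe: minutes to fall asleep, number of awakenings, and time to fall back asleep. Caregiver completion is plausible here, since Section 4.1 admits patients with Karnofsky 60% and allows consent through a legally authorized representative.
- Staff following Section 7.1 and staff following Section 7.6 would collect different records in the middle of fixed dosing. That changes the amount of actigraphy available to the dose-gradient regression.

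**Working it through.** The plan gives no sample size, power or effect size for the diary, so there is no stated figure to reproduce. The check is a comparison of texts and a count of nominal study days.

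**1. Which Appendix R fields are affected by the scale error**

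| Field type | Examples | Options fit? |
|---|---|---|
| Clock time, duration, count | nap length, time entered bed, minutes to fall asleep, awakenings, wake time, time out of bed | Not affected |
| Rating: falling asleep, staying asleep | extremely difficult to very easy | Yes |
| Rating: quality, comparison with other nights | extremely difficult to very easy | No |

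Two of the four rating items are mismatched. The same options repeat across the day columns for both items, so a text-extraction error is unlikely.

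**2. Diary days under each schedule**

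- Section 7.1, continuous: D1-D70 = 70 days.
- Section 7.2 footnote h: D1-7 (7) + D8-28 (21) + D29-35 (7) + D63-70 (8) = 43 days. 43/70 = 61%.
- Difference: 70 − 43 = 27 days, which are D36 to D62 (62 − 36 + 1 = 27).

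The baseline week (D1-7) and the last week (D64-70) fall in both sets. Actigraphy is also collected in both weeks under either version, since Section 7.1 includes a baseline actigraphy week. The conflict therefore removes no day from a baseline versus last-week comparison.

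**3. Actigraphy days by dose, for a patient who reaches and stays on 300 mg**

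- 75 mg: D8-14 = 7 days under either version.
- 150 mg: D15-21 = 7 days under either version.
- 300 mg, continuous: D22-D70 = 70 − 22 + 1 = 49 days.
- 300 mg, windowed: D22-28 (7) + D29-35 (7) + D63-70 (8) = 22 days, or 21 if the last window is exactly seven days.

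Each escalation week is covered either way. The two versions differ only in how much fixed-dose actigraphy exists, and Section 13.3.1 does not say which days enter the regression.

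**4. Reporter**

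No count is possible, because the documents do not say how often caregivers would complete the diary or how often the reporter would change.

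**The case against.** The strongest reply is that none of this reaches the stated objective. Objective 6 concerns sleep-wake times, which Appendix R holds in separate fields. Sleep quality has its own objective and instrument, the PSQI. The two faulty items feed no named endpoint, and their options are at least ordered and the same before and after. Both schedules cover the weeks that matter. Actigraphy runs alongside the diary in those weeks and gives an objective comparator. Section 7.8 also does not say whether a caregiver gives an independent judgement or only writes down the patient's answers.

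Most of this stands, and it limits the point. Three things remain:

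- A consistent wrong scale still does not yield a rating of quality or of better versus worse.
- Actigraphy may expose a gross shift in diary times, but it does not show who filled in the form, so the check is indirect.
- The schedule texts contradict each other, and the dose-gradient analysis has no stated window.

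A reader might also bring in the pilot's patient-caregiver correlation of 0.56, reported with the remark "though important differences were present at the extremes of patient ESS". That figure is for the ESS, a dozing-likelihood rating, in a one-time survey. It does not measure agreement on bedtimes or awakenings, and the plan itself reads it as support for self-report. It cannot size the reporter effect in the diary.

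**Conclusion.** The point holds as three correctable defects: two unreadable ratings, an unrecorded reporter, and a schedule conflict over 27 days per patient (D36-D62). For a patient who stays on 300 mg, the conflict changes actigraphy at that dose from 49 days to about 22.

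A reader might infer that the diary's pre-post change is uninterpretable. The documents do not support that. The scale error leaves every time, duration and count field intact. The schedules agree on the baseline and last fixed-dose weeks. An unrecorded reporter is a risk of bias if the reporter changes, not proof that every diary variable is void.

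A reader might also count lost answers: 6 weeks × 7 nights × 36 patients × 2 items = 3,024. That is an upper bound on items no stated endpoint uses. It assumes all 36 patients complete every diary week, while Section 13.4 expects at least 33 to reach 150 mg and at least 30 to reach 300 mg.

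The verdict assumes that Appendix R as shown is the form in use, that nominal days apply without the visit windows, and that pre-post means baseline week against last fixed-dose week. Section 13 does not define that window. The size of any reporter bias is unknown.

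**What to change.** 1. **Appendix R ratings.** Give the quality item options from very poor to very good, and the comparison item options from much worse to much better.
2. **Reporter.** Add a line to each diary week recording whether the patient or a caregiver completed it. Ask for the same reporter at baseline and in the last fixed-dose week where possible. Reconcile the caregiver permission in Section 7.8 with the patient-reported definition in Section 6.2. Keep all pairs in the main analysis and add a same-reporter sensitivity analysis. Restricting the main analysis to same-reporter pairs would be worse: patients who hand the diary to a caregiver may be those who are declining, so excluding them could be informative.
3. **Schedule.** Reconcile Section 7.1 with Section 7.2 footnote h, Section 7.6 and both statements in Section 7.8, item 2, so that all say the same about which record is continuous. State in Section 13.3.1 which actigraphy days enter the dose-gradient analysis.

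The cost is one form revision with one extra field, a few text edits, and one extra analysis. Answers already given on the present form to the two mismatched items cannot be converted.
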